10.0 Criteria for Termination

10.1 Conditions for Terminating the Study

The Principal Investigator may terminate the study for any of the following reasons:

- Significant toxicities: Patients with any grade 3/4 toxicity that persists and does not improve 21 days after discontinuation of all study medications, despite pharmacologic management, will be removed from the study. Any patient who experiences any grade 4 toxicity can be removed from the study at the discretion of the study investigator.
- If it becomes clear that the study treatment is less effective than standard treatment. The phase II study has a two-stage design (see section 3 for more details). If fewer than 8 out of the first 20 pts are progression-free at 12 weeks, this would be considered an unacceptably low PFS rate (<39%), the study will not continue and accrual will cease. Study accrual will continue while efficacy is being determined. Conversely, if at least 7 patients in the first stage of the phase II study are free of progressive disease at 12 weeks, then enrollment will continue to the second stage of the study. .
- Once all data collection has been completed.

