For Phase II, sample size is based under the Simon's 2-stage optimal design for progression-free survival at 3 months as a single proportion. The study is designed to determine the following hypothesis with >80% power and 2-sided type I error of 5% using binomial approximation: H₀: PFS% <39% versus H_a: PFS% > 57% (with PLX3397), where PFS% is the proportion of progression-free (PFS) at 3 months. The PFS% of >57% would represent a clinically relevant improvement with the treatment in triple-negative patients with locally recurrent or metastatic breast cancer. Based on these considerations, a sample size of 51 evaluable patients is required for the study. We plan for a targeted enrollment of 56 patients with 10% dropout rate.

Interim assessment and stopping rules for Safety and efficacy

Safety and SAE data will be routinely monitored. Because of the possibility of unacceptable or excessive defined serious adverse events during treatment or the study enrollment period, stopping rules for safety/tolerability are also developed. We have set the maximum rate of treatment-related SAE at 15% in patient enrollment. Thus, we may consider terminating the study if the number of patients with SAE is greater than the number expected under the binomial distribution. The following table shows the early stopping guideline based on the number of SAE observed under the rate of unacceptable SAE in the group sequential enrolment for the study. For example, assuming the unacceptable rate of SAE is greater than 15%, if the study observes 3 or more SAE in the first 17 treated patients, then we may consider if the study should be stopped early.

Safety Stopping Rules:

Number of enrolled patients with excessive SAE to consider early study termination.

Number patients in study	1-17	18-29	30-41
Unacceptable SAE – 15%	3	4	6

Efficacy Stopping Rules

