Failure to obtain early responses at the scheduled tumor assessments will be taken as evidence that the regimen in question is ineffective. If fewer than 8 out of the first 20 pts are progression-free at 12 weeks, this would be considered an unacceptably low PFS rate (<39%), the study will not continue and accrual will cease. Accrual will continue while efficacy data is being determined. If 25 or fewer pts are progression free at 12 weeks at full accrual, then the treatment would be deemed ineffective. If the true PFS rate at 12 weeks is 39% for TNBC pts, the probability of terminating the study during the interim evaluation is 0.63; if the true PFS rate is 57% for TNBC pts, the probability that the trial will be stopped in the first stage is 0.10.

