12.3 Accrual Objectives

Phase I

A minimum of 12 patients will enroll in the Phase I trial, following a 3+3 design for 3 cohorts. We estimate that 10 patients will enroll at UCSF, and 7 patients each at Duke and Vanderbilt. Phase I completed at UCSF with 28 patients enrolled as 03/10/2015

Phase II

This study will enroll 56 patients (n=22 in the first stage and n=34 in the second stage) in the Phase II portion with the assumed 10% dropouts. We estimate that 26 patients will enroll at UCSF and 15 each at Vanderbilt and Duke.

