12.4 Estimated Duration of Study

The Phase I study is expected to complete accrual within 1.25 years, and the Phase II study is expected to complete accrual over a time course of 2.5 years.

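### Accrual stays open during the stage-1 futility look, with no rule to stop it once the continuation threshold is out of reach; a trial that stops enrols about 3 to 4 patients after that point

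*Combined protocol and SAP*

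**What the plan says.** Section 12.1 (Efficacy Stopping Rules) ends the study "If fewer than 8 out of the first 20 pts are progression-free at 12 weeks" and then states "Accrual will continue while efficacy data is being determined". Section 10.1 gives the same rule with "Study accrual will continue while efficacy is being determined", but adds that enrolment goes on to stage 2 "if at least 7 patients in the first stage of the phase II study are free of progressive disease at 12 weeks". Neither section has a curtailment rule, a pause in accrual or a cap on the overrun.

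Other relevant statements:
- Section 12.4: "the Phase II study is expected to complete accrual over a time course of 2.5 years".
- Section 12.3: "This study will enroll 56 patients (n=22 in the first stage and n=34 in the second stage". The futility rule itself counts 20.
- Section 12.1: hypotheses "H₀: PFS% <39% versus H_a: PFS% > 57" (per cent), with ">80% power and 2-sided type I error of 5% using binomial approximation"; 51 evaluable patients; a final limit of 25 progression-free patients or fewer; early-stop probabilities of 0.63 at 39% and 0.10 at 57%; CT every 6 weeks.
- Section 12.2: a missing 12-week assessment counts as a failure.
- Section 12.6: some patients who leave early for reasons other than progression or toxicity are replaced.

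**The concern.** A progression can show at the week-6 scan, whereas a success is known only at week 12. Failures therefore tend to accumulate ahead of successes, and the stage-1 result can be settled before the 20th patient's week-12 scan. If accrual simply runs until that scan, patients with metastatic triple-negative disease enter, and are asked for biopsies, after the trial can no longer meet its own criterion. Their entry adds nothing to the stage-1 decision. Ending accrual when the outcome is fixed (deterministic curtailment) spares them without changing that decision.

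**Working it through.** **1. Reproduce the plan's figures.** Exact binomial for stage 1 with n = 20, then two-stage enumeration with a final limit of ≤25 of 51:

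| Stop at stage 1 if | Source | P(stop), 39% | P(stop), 57% | One-sided alpha | Power | Stop certain at failure |
|---|---|---|---|---|---|---|
| ≤6 | implied by the continue rule in 10.1 | 0.280 | 0.014 | 0.054 | 0.841 | 20 − 6 = 14th |
| ≤7 | fewer than 8, in 12.1 and 10.1 | 0.452 | 0.040 | 0.053 | 0.831 | 20 − 7 = 13th |
| ≤8 | implied by the stated 0.63 and 0.10 | 0.631 | 0.096 | 0.048 | 0.801 | 20 − 8 = 12th |

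The stated 0.63 and 0.10 reproduce only with ≤8, and the 5% error only as one-sided. The text therefore supports three different limits, and the failure that settles stage 1 differs between them.

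**2. Accrual.** 56 / 2.5 = 22.4 patients a year, or 1.87 a month. Twelve weeks is 84 / 30.4375 = 2.76 months, so about 1.87 × 2.76 = 5.2 patients enter in the 12 weeks after patient 20.

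**3. When failures are seen.** The documents do not give the share seen at week 6. With a constant hazard and 39% progression-free at week 12, the share is (1 − √0.39) / (1 − 0.39) = 0.3755 / 0.61 = 0.616.

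**4. Patients entered after the stop is certain.** Simulation of 20,000 trials with random (Poisson) entry at 22.4 a year, true rate 39%, scans at weeks 6 and 12, no data lag, and the look when patient 20 reaches week 12. Results are for trials that stop at stage 1; differences were taken before rounding.

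| Limit | Enrolled at the look | Enrolled when certain | Difference | Days earlier |
|---|---|---|---|---|
| ≤6 | 25.2 | 22.4 | 2.7 | 44 |
| ≤7 | 25.1 | 21.9 | 3.2 | 53 |
| ≤8 | 25.2 | 21.2 | 4.0 | 64 |

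About 15–25% of stopping trials save nobody.

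**5. Sensitivity** (limit ≤7; each range covers random and even entry).
- Week-6 share: 1.8–1.9 if no failure shows before week 12, 2.9–3.2 if half do, 4.5–4.9 if all do. Across the three limits the span is about 1.4 to 5.
- True rate, constant hazard: 4.2–4.5 at 30%, 2.8–3.1 at 45%, 2.2–2.5 at 57%.
- Accrual rate, random entry: 2.9 at 16 a year, 3.6 at 28 a year.
- Look taken as soon as all 20 outcomes are known: 2.7–2.8.

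**6. Averaged over all trials.** Under the written rule at 39%: 0.452 × 3.25 ≈ 1.5, where 3.25 = 25.12 − 21.87 is the ≤7 difference before rounding.

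**7. Stage 2.** With 51 evaluable patients the final threshold is 26 successes, so 51 − 25 = 26 failures settle it. A trial that passes stage 1 and then fails would end accrual at a mean of 47.3 (limit ≤7) or 48.1 (limit ≤8) instead of 51. If the final count is taken over all 56 enrolled, 26 failures still leave 30 possible successes and nothing is settled; the trigger would be 56 − 25 = 31.

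**The case against.** A two-stage design without curtailment is standard, and the protocol openly chose uninterrupted accrual. A reader might infer that the rule forces the trial to wait for patient 20's week-12 scan. The documents do not say so; it is the natural reading, not an instruction. Section 10.1 lets the Principal Investigator terminate if the treatment is clearly less effective than standard, and section 16.2 requires continuous data review by the Study Chair. Earlier action is therefore allowed. What stands is that nothing requires it or says when.

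A reader might also infer that the 13th failure always settles stage 1. Under the continue rule in 10.1 it does not, because seven successes are still possible and that rule continues at seven.

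Nor is every tallied failure final. A patient with no 12-week assessment counts as a failure under 12.2 but may be replaced under 12.6, PFS is analysed in the Per Protocol population, and 12.3 enrols 22 rather than 20 in stage 1. A claim that the decision and error rates are untouched therefore holds only for a fixed evaluable set with settled outcomes. This limits how the rule is worded; it does not remove the case for one.

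Finally, 3 to 4 patients is not the expected saving in every trial. It applies only when stage 1 stops.

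**Conclusion.** The gap is real and small. Sections 10.1 and 12.1 keep accrual open and do not end it when the threshold becomes unattainable. In a trial that stops at stage 1, with a true rate of 39%, planned accrual and a constant hazard, about 3 to 4 patients enter after the stop is certain. Such a stop has probability 45% at that rate under the written rule, and 63% under the limit that reproduces the plan's own figures. The least certain input is the week-6 share of failures, which the documents do not give. This is an optional improvement, secondary to reconciling the stage-1 limit; it does not make the design invalid.

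**What to change.** First reconcile the stage-1 limit (fewer than 8 to stop, at least 7 to continue, or the 8 or fewer implied by 0.63 and 0.10), the stage-1 size (20 or 22) and the final denominator (51 or 56). Then add to sections 12.1 and 10.1 a sentence such as:

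> Accrual stops as soon as confirmed 12-week failures among the first 20 evaluable patients, excluding those to be replaced under section 12.6, make the stage-1 continuation threshold unattainable. The same applies in stage 2 to the final threshold among the evaluable patients (26 failures if the denominator is 51).

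Tie the stage-1 trigger to the threshold rather than to a fixed count, and change 20 if the reconciled stage-1 size differs. The sentence concerns accrual only; patients already on treatment continue as the protocol provides.

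The cost is one sentence and a running tally, which is feasible because the trial is open label and section 12.1 already sets running SAE thresholds. At whichever limit is adopted, and for a fixed evaluable set, the decision, type I error, power and early-stop probability do not change. The downside is a few fewer patients for response rate and safety in a trial that stops anyway.

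### The final limit of 25 is calibrated to 51 evaluable patients but applied at full accrual (56) with no denominator, and the written interim rules do not give the stated error rates

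*Combined protocol and SAP*

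**What the plan says.** **Sample size (12.1).** Phase II tests a 12-week (3-month) progression-free proportion of 39% against 57% in a Simon two-stage design with more than 80% power and a "2-sided type I error of 5% using binomial approximation". From this, "a sample size of 51 evaluable patients is required for the study", and "We plan for a targeted enrollment of 56 patients with 10% dropout rate".

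**Stage sizes (12.3).** "This study will enroll 56 patients (n=22 in the first stage and n=34 in the second stage").

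**Interim rule.** Sections 10.1 and 12.1 both stop accrual on this condition: "If fewer than 8 out of the first 20 pts are progression-free at 12 weeks". The same bullet in 10.1 also lets enrolment go on to the second stage "if at least 7 patients in the first stage of the phase II study are free of progressive disease at 12 weeks". Under a true rate of 39%, 12.1 says that "the probability of terminating the study during the interim evaluation is 0.63"; under 57% it gives 0.10.

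**Final rule (12.1).** "If 25 or fewer pts are progression free at 12 weeks at full accrual, then the treatment would be deemed ineffective". No denominator is given.

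**Who is counted.** Section 12.2 analyses PFS in a Per Protocol population that the documents do not define, and scores a patient without the 12-week assessment as a failure. Section 12.6 replaces some patients who stop early for reasons other than progression or toxicity, without saying whether those replaced stay in the denominator. Section 9.1 defines evaluability for toxicity, objective response and non-target disease, but not for 12-week PFS.

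**The concern.** Success means 26 or more patients progression-free, whatever the number analysed. A fixed count has the intended error rates only at the number for which it was derived. Twenty-six successes are easier to reach among 54 assessed patients than among 51, and harder if some of the 51 are unassessed and scored as failures. The final rule points to 56, the sample-size paragraph to 51, and the rules on missing assessments, replacement and analysis population do not settle which number applies.

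The interim limit matters too, because stopping early removes some false positives. If the limit in the text is not the one behind the stated probabilities, the quoted properties do not describe the trial that will be run. At stake is the false-positive risk and power of the decision on whether the combination deserves further study.

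**Working it through.** **Inputs.** p0 = 0.39, p1 = 0.57, 51 evaluable, 56 enrolled, 10% dropout, final limit 25 (12.1); stages of 22 and 34 (12.3); interim on 20 (10.1 and 12.1). Three interim readings are carried: stop at 8 or fewer (the reading tested against 0.63/0.10), at 7 or fewer (the written stop below 8), and at 6 or fewer (the 10.1 rule that 7 continue, read on the same 20).

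**Formulas.** With X1 ~ Bin(20, p) and interim limit r1:
- P(stop early) = P(X1 ≤ r1)
- P(declare success) = Σ over x from r1+1 to 20 of P(X1 = x) · P(Bin(N − 20, p) ≥ 26 − x)

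The second gives one-sided alpha at p = 0.39 and power at p = 0.57.

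**Step 1: reproduce the plan (N = 51).**

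| Interim stop | Early stop at 39% / 57% | Alpha | Power |
|---|---|---|---|
| 8 or fewer | 0.631 / 0.096 | 0.048 | 0.801 |
| 7 or fewer | 0.452 / 0.040 | 0.053 | 0.831 |
| 6 or fewer | 0.280 / 0.014 | 0.054 | 0.841 |

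Only the first row gives the stated 0.63/0.10. It also gives power above 80% and one-sided alpha below 5%. The stage sizes agree with 51: 22 × 0.9 = 19.8 and 34 × 0.9 = 30.6, about 20 + 31.

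**Step 2: hold the limit at 25 and vary the number assessed.** One-sided alpha:

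| Assessed | Stop ≤8 | Stop ≤7 | Stop ≤6 |
|---|---|---|---|
| 51 | 0.048 | 0.053 | 0.054 |
| 52 | 0.060 | 0.066 | 0.069 |
| 53 | 0.073 | 0.082 | 0.086 |
| 54 | 0.088 | 0.100 | 0.106 |
| 56 | 0.120 | 0.141 | 0.152 |

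**Step 3: planned dropout, missing scored as failure.** Missingness is assumed independent of outcome.
- Twenty assessed at the interim and 10% of the 34 second-stage patients missing (N = 54, second-stage rate 0.9p): alpha 0.046 / 0.051 / 0.053, power 0.78 / 0.81 / 0.82 (order ≤8 / ≤7 / ≤6).
- Ten per cent of all 56 missing (rate 0.9p throughout): alpha 0.039–0.051, power 0.69–0.79. This is pessimistic, since 12.6 replaces some of these patients and some would have been failures anyway.

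**Step 4: denominator fixed at 51, share m unassessed and scored as failure.** The rate becomes p(1 − m).

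| m | Power (≤8 / ≤7 / ≤6) |
|---|---|
| 0 | 0.80 / 0.83 / 0.84 |
| 2% | 0.76 / 0.79 / 0.80 |
| 5% | 0.68 / 0.71 / 0.72 |
| 10% | 0.53 / 0.56 / 0.57 |

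**Step 5: two-sided 5%.** This allows 0.025 in the upper tail. At N = 51 the limit of 25 gives 0.048–0.054, about twice that. A limit of 26 gives 0.028–0.030 with power 0.74–0.77. A limit of 27 gives 0.015 with power 0.65–0.67.

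**The case against.** The calculation behind 25 is not wrong. With 8 of 20 and 25 of 51 it reproduces the stated early-stopping figures and power, and 51 can be inferred from the sample-size paragraph and from 22 + 34 less 10%. The reference to full accrual may only mark the time of the final look, in contrast to the first 20 patients. At the planned dropout alpha is close to 5%. The interim conflict and the sidedness are separate faults that would exist with a clear denominator. Section 12.2 also refers to an SAP for some detail, so a fuller population definition may have been intended.

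Most of this stands, and it limits the point. A reader might infer that the true false-positive rate is 12–15% because 25 is applied to 56. The documents do not support that: it needs all 56 assessed, hence zero dropout against a planned 10%. The 0.069 at 52 rests on the 10.1 wording that 7 continue, which the same bullet contradicts. Nor do the documents show that anyone intends to choose the denominator after seeing outcomes; 12.2 already prescribes missing as failure, and enrolment is capped at 56 apart from replacements.

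What the objection does not remove is that the decision rule itself omits 51 and no other rule delivers it. The written interim limits also contradict the probabilities quoted beside them. The interim limit has to be settled together with the final one, because alpha at 51 depends on both.

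**Conclusion.** The point holds as a mismatch between the written decision rules and their stated properties, not as an error in deriving 25. If exactly 51 are assessed, or at roughly the planned dropout, one-sided alpha is about 0.05. Each assessed patient above 51 adds about 0.01 to 0.02. On the reading that reproduces 0.63/0.10, alpha is 0.060 at 52, 0.088 at 54 and 0.120 at 56; under the written stop below 8 it is 0.066, 0.100 and 0.141.

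Neither written interim rule gives 0.63/0.10: they give 0.45/0.04 and 0.28/0.01, with alpha 0.053 and 0.054 at 51. No reading meets a two-sided 5%.

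These figures assume an interim on 20 assessed patients and exact binomial outcomes. Those with missing data also assume missingness unrelated to outcome. This should be corrected in the text; it does not invalidate the design.

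**What to change.** 1. **Interim limit and sidedness (10.1, 12.1).** Reconcile the two wordings with 0.63/0.10. State the early-stopping probabilities, alpha and power for the limit kept, and say that the 5% is one-sided. Of the three readings, only 8 or fewer of 20 keeps alpha at or below 5% with limit 25 of 51.

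2. **Denominator (12.1).** Replace the reference to full accrual with the first 51 evaluable patients in enrolment order. Alternatively, prespecify the limit by number analysed. With the interim at 8 or fewer of 20:

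| Analysed | Ineffective at or below | Alpha | Power |
|---|---|---|---|
| 51 | 25 | 0.048 | 0.80 |
| 52 | 26 | 0.036 | 0.77 |
| 53 | 26 | 0.045 | 0.80 |
| 54 | 27 | 0.033 | 0.78 |
| 55 | 27 | 0.042 | 0.81 |
| 56 | 28 | 0.031 | 0.78 |

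3. **Analysis set (12.2, 12.6).** Before the data are seen, define the set for the primary proportion in place of the undefined Per Protocol population, and say whether replaced patients stay in it. Excluding them is less conservative than the missing-as-failure rule in 12.2. If that is chosen, say so and report a sensitivity analysis counting them as failures.

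4. **Power.** State it under missing-as-failure over a plausible range, not only at a low rate. At 51 it is about 0.76–0.80 with 2% unassessed, 0.68–0.72 with 5% and 0.53–0.57 with 10%. Fixing the denominator at 51 while still scoring unassessed patients as failures uses up the allowance between 51 and 56, so this loss must be shown.

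**Cost.** These are wording changes with no extra patients. The price is that the stated power may have to be given as below 80%. Keeping it above 80% with missing scored as failure would mean re-deriving the limits and possibly the sample size.

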12.2 Analysis Plan

Primary Efficacy Endpoint

Demographics and Baseline Characteristics

Demographic data (age, sex, race, ethnicity, body weight) and baseline disease characteristics will be tabulated and summarized and presented in data listings.

Progression Free Survival

Progression-free survival at 3 months (PFS) is defined as the proportion of patients alive and progression-free 90 days after Study Day 1. Duration of PFS is defined as the time from Study Day 1 to the earlier of disease progression or death due to any cause.

Progression free survival will be calculated from the first administration of PLX3397 with eribulin. The analyses of PFS will be performed using the Per Protocol population. These analyses are designed to include only objective progression events per the RECIST v1.1 criteria. Patients who do not have any post-baseline tumor assessments will be right censored on the date of Study Day 1. Patients who receive subsequent anti-cancer therapy before experiencing an event will be right censored at the date of the last tumor assessment prior to the date of initiation of subsequent therapy. Patients who have not experienced an event (and are not otherwise censored) at the time of data cutoff will be right censored on the date of their last tumor assessment

PFS will be estimated as a simple proportion based upon the results of the 12-week tumor assessment. Patients for whom this assessment is not performed will be included as failures, even if known to be alive at this timepoint. Confidence intervals will be provided. PFS and duration of PFS will also be estimated using Kaplan-Meier methods with associated confidence intervals.

Secondary and Supportive Efficacy Endpoints

Objective Response Rate

The objective response rate (ORR) is defined as the proportion of patients for whom the best overall response at the time of data cutoff is confirmed CR or confirmed PR as assessed per RECIST v 1.1 criteria. A table defining the derivation of best overall response to be applied will be provided in the SAP.

The analysis of ORR will employ the Per Protocol population. Patients who do not have any post-baseline tumor assessments will be counted as non-responders.

Point estimates of ORR and confidence intervals will be provided. As a basic measure of dose-response, ORR in the escalation phase will also be presented by dose cohort. Objective response will be assessed using the RECIST v 1.1 response criteria. The response will be collected on CRFs. The number and percent of subjects with each type of response will be summarized and presented in data listings. A 95% confidence interval will also be calculated using exact binomial method. The 95% confidence interval for the difference in objective response rates will be calculated using exact binomial method. Time to onset of the response and duration of response will be also summarized using descriptive statistics.

Duration of Response

Duration of response is defined as the time from first documentation of objective response that is subsequently confirmed to PD by the criteria or death due to any cause. Responders who have not been documented to have progressed or died at time of data cutoff will be right censored at the last available adequate tumor assessment. Median duration of response for each treatment arm and its associated confidence interval will be estimated using the Kaplan-Meier method.

Time to Progression

Time to progression will be estimated using the Kaplan-Meier method. Efficacy responses, disease progression and relapse classified based on RECIST v1.1 criteria will be used to determine progression. Time to progression will be calculated from the first administration of PLX3397 with eribulin. Patients who do not have disease progression will be censored at the date of the last evaluation for study disease or at the time of initiation of the new therapy, whichever is earlier. Patients lacking any response assessment after randomization will be censored at Day 1.

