Due to the bone marrow suppression known to occur with eribulin, patients may receive myeloid growth factors at any time, at physician discretion (for guidelines regarding use of neupogen, see section 6.1). An eribulin premedication regimen of intravenous dexamethasone (6 mg, or physician-selected dose), or other equivalent steroid, <60 minutes prior to eribulin. This may be tapered with subsequent doses per investigator discretion.

Note: Patients enrolled on to the trial under protocol version 6.0 which allowed for Eribulin dosing schedule of Day 1 and Day 15 every 28 days will remain on that treatment and assessment schedule.

Phase II: The phase II portion will begin after the MTD for PLX3397 is determined and we will enroll a total of 56 patients with triple (ER/PR/HER2) negative metastatic breast cancer to evaluate the safety and efficacy of the proposed treatment. In the phase II study, treatment is preceded by a 6 to 7 day lead-in phase, in which patients will take PLX3397 800mg (400 mg in the morning and 400 mg at night) alone for 5 days, followed by 1 to 2 days off before starting eribulin combined with PLX3397. PLX3397 will continue to be given on a 5 days on, 2 days off schedule, repeated weekly, throughout the course of treatment. Concomitant antihistamines are recommended to reduce the incidence of rash. A tumor core biopsy will be obtained before treatment start, and then again before the start of eribulin. Patients will be treated until clinical or radiographic disease progression or cumulative toxicity and will be evaluated regularly in clinic. Evaluation of disease response or progression will be accomplished with CT scans, and bone scans as indicated, every 6 weeks. Visits will take place before each dose of eribulin (Day 1 and Day 8) during cycle 1, and then on Day 1 before cycle 2 and beyond.

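### The Kaplan-Meier PFS rule censors every unscanned patient at Day 1 with no exception for death, so the supportive curve is biased upward if early deaths or undocumented failures occur

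*Combined protocol and SAP*

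**What the plan says.** All the rules are in section 12.2 of the combined protocol and SAP.

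- **Definition.** "Duration of PFS is defined as the time from Study Day 1 to the earlier of disease progression or death due to any cause".
- **Type of progression.** "These analyses are designed to include only objective progression events per the RECIST v1.1 criteria".
- **No scan (Kaplan-Meier PFS).** "Patients who do not have any post-baseline tumor assessments will be right censored on the date of Study Day 1". This sentence covers every unscanned patient. The two censoring sentences that follow it, on new therapy and on data cutoff, apply only to patients who have not had an event.
- **New therapy before an event (PFS).** Such patients "will be right censored at the date of the last tumor assessment prior to the date of initiation of subsequent therapy".
- **TTP.** Patients without progression are "censored at the date of the last evaluation for study disease or at the time of initiation of the new therapy, whichever is earlier". For those never assessed: "Patients lacking any response assessment after randomization will be censored at Day 1". Death is not named as a TTP event.
- **Primary proportion.** PFS is estimated as a simple proportion from the 12-week scan. "Patients for whom this assessment is not performed will be included as failures, even if known to be alive at this timepoint". Kaplan-Meier is an additional estimate.

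Section 5.1 (Phase II) says: "Patients will be treated until clinical or radiographic disease progression or cumulative toxicity". Section 12.1 repeats this. Section 5.2 instead ties the end of treatment to progression by RECIST v1.1. These passages must be reconciled; this point takes no view on which should govern.

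**The concern.** Kaplan-Meier estimation is unbiased only if censored patients have the same outlook as those still at risk. Two groups here plainly may not: patients who die or deteriorate before the week-6 scan, and patients who stop on clinical grounds with no scan that meets RECIST progression. The first group is set to time 0 and the second to the last scan, just as they fail. Under the definition of PFS, the deaths among them should be events.

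What is at stake is the Kaplan-Meier 3-month rate, median PFS and the TTP curve. The medians come only from these curves, and readers usually compare medians with published figures. Section 12.2 plans no sensitivity analysis of the censoring.

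**Working it through.** **Plan's own figure.** There is none for the Kaplan-Meier analysis. The inputs below are the null 39%, the alternative 57% and 51 evaluable patients (all section 12.1), with scans every 6 weeks (section 8.2.3).

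**Step 1: the rules side by side.**

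| Patient | 12-week proportion | Kaplan-Meier PFS | TTP |
|---|---|---|---|
| Dies before any scan | failure | event by the definition, censored at Day 1 by the rule | censored at Day 1 (death is not an event) |
| Stops for clinical progression, never scanned | failure | censored at Day 1 | censored at Day 1 |
| Clinical progression after the week-6 scan, no RECIST documentation, no 12-week scan | failure | censored at last scan, unless a death is recorded before new therapy | censored at the earlier of last evaluation and new therapy |

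The first row is a conflict within the text. The other two follow from the rules as written.

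**Step 2: censoring at time 0 is exclusion.** The estimate is the product of (1 - d/n) over event times, where n counts patients still at risk. A patient censored at time 0 is in no n. If a fraction q of all patients fails unscanned by week 12, and there is no other censoring, a true rate S is estimated as S/(1 - q).

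| Assumed q | True 39% | True 57% |
|---|---|---|
| 5% | 0.39/0.95 = 0.411 | 0.57/0.95 = 0.600 |
| 10% | 0.39/0.90 = 0.433 | 0.57/0.90 = 0.633 |

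At a true 39%, 61% of patients fail by week 12, so q of 5% to 10% means that 5/61 = 8% to 10/61 = 16% of failures are unscanned.

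**Step 3: the same in counts.** With 20 of 51 progression-free, the proportion is 39.2%. If 5 of the 31 failures had no scan, Kaplan-Meier gives 20/46 = 43.5%. If 8 had none, it gives 20/43 = 46.5%.

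**Step 4: censoring at the last scan.** Suppose a fraction c of patients progresses clinically after the week-6 scan and is censored there. Split the documented failures equally between weeks 6 and 12, so e = (1 - S - c)/2. Then the estimate is (1 - e) x (1 - e/(1 - e - c)).

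- S = 0.39, c = 5%: e = 0.28, giving 0.72 x (1 - 0.28/0.67) = 0.419.
- S = 0.39, c = 10%: e = 0.255, giving 0.745 x (1 - 0.255/0.645) = 0.450.
- S = 0.57: 0.607 for c = 5% and 0.648 for c = 10%.

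**Step 5: both routes together.** A simulation used exponential PFS, 6-weekly scans, 51 patients and 2,000 runs per scenario. Undocumented failures before week 6 were censored at Day 1 and later ones at the last scan.

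| Failures undocumented (assumed) | True 39% | True 57% |
|---|---|---|
| 10% | 0.421 | 0.599 |
| 20% | 0.457 | 0.631 |
| 30% | 0.495 | 0.662 |

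Counting all these failures as events returned the true values, 0.39 and 0.57.

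**Step 6: who stays unscanned.** Section 12.6 replaces patients with no evaluation who stop for reasons other than progression or toxicity. Those left unscanned and not replaced are therefore mainly patients who stopped for progression or toxicity, which supports the upward direction. Early failure is also common in this disease: section 1.2 gives a PFS of 2.23 months for eribulin in triple-negative patients. If that is a median and PFS is exponential, 1 - 2^(-1.38/2.23) = 35% progress or die within 6 weeks (1.38 months). How many of them would go unscanned is not known.

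**The case against.** The strongest reply is that nothing decisive depends on these curves. The hypothesis in section 12.1 is about a single proportion, both stopping boundaries are counts of patients progression-free at 12 weeks, and a missing scan counts as failure. Median PFS and TTP are not among the Phase II objectives in sections 2.1.2 and 2.2.2. This stands. A reader might infer that the primary result or the go/no-go decision is inflated; the documents do not support that.

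Second, the definition names death as an event, and restricting events to objective progression can be read as limiting the kind of progression without excluding death. This partly stands: the plan does not expressly say that deaths are censored. But the Day 1 sentence, unlike its neighbours, is not confined to patients without an event, so a programmer following it literally would censor them.

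Third, a reader might extend the objection about deaths to TTP. Death is not a TTP event, so censoring deaths there follows the endpoint. Only undocumented progressions are at issue for TTP.

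Fourth, the plan has safeguards: an end-of-treatment scan (section 8.2.3), an instruction in section 9.1 to try to document progression after symptomatic deterioration, and a required life expectancy of at least 12 weeks (section 3.2). These should reduce the number of patients affected. They do not help patients who die or are too ill to be scanned, and they do not change the rule.

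Fifth, a reader might take any gap between the proportion and the Kaplan-Meier rate as the bias. It is not: the proportion also fails patients who are alive and merely unscanned, so it is conservative by design.

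**Conclusion.** The point holds for the supportive analyses only. The Day 1 rule conflicts with the definition of duration of PFS for deaths before the first scan. With RECIST-only progression, the rules also remove or censor early the patients who fail without documentation. If such patients occur and have a worse outlook than those still at risk, the Kaplan-Meier 3-month rate and median PFS are biased upward. For TTP the same holds for undocumented progressions alone.

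The direction is well supported; the size is not. The documents give a 10% dropout rate but do not link it to failure. Assuming that 5% to 10% of patients fail unscanned and are censored at Day 1, the 3-month rate is overstated by about 2 to 4 points at a true 39% and 3 to 6 points at a true 57%. Undocumented clinical progression after a scan would add to this. For scale, the standard error of a proportion of 39% in 51 patients is sqrt(0.39 x 0.61/51) = 0.068, so these Day 1 shifts are within one standard error. They are systematic, however, and can be avoided.

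**What to change.** In section 12.2, under Progression Free Survival:

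1. State that death from any cause at any time, including before the first scan, is a PFS event on the date of death, and that only unscanned patients who are not known to have died are censored at Day 1. Say also whether the new-therapy censoring rule takes precedence for a death after new therapy has started, so that the two sentences do not collide.
2. Add one sensitivity Kaplan-Meier analysis, for PFS and for TTP, that counts clinical progression and the start of new anti-cancer therapy as events. Item 1 restores only the deaths; this analysis shows how far undocumented progression moves the curves.

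While editing the TTP rule, replace its reference to randomization, since the study is nonrandomized. The primary proportion needs no change.

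The cost is a few sentences and one additional analysis, with no extra patients, visits or scans. The date of clinical progression must be recorded if the CRF does not already capture it; the start date of new therapy is already needed for the existing rules. The reported median PFS may be slightly shorter.
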